12.3.1.1. Demographic/Medical History

Demographic information, a complete medical history (which includes surgical history), and medication history will be collected at the screening visit by appropriate site staff as delegated by the PI and reviewed and verified by a qualified licensed physician, physician's assistant, or a nurse practitioner. The medical history will be reviewed and recorded, including:

- Date of birth
- Sex
- Race and ethnicity
- Recent use of non-CD/UC medication within 30 days of Visit 1
- CD/UC past and ongoing treatments (recall past year)
- CD/UC-related surgical procedures and hospitalizations
- History of respiratory, cardiovascular, renal, gastrointestinal, hepatic, endocrine, hematological, neurological, psychiatric, and other diseases; history of surgical procedures

12.3.1.2. Vital Signs

Vital signs, including systolic and diastolic blood pressure, pulse, and respiration rate, will be collected as shown in the Schedule of Assessments (see [Table 1](#)). Vital signs must be within the ranges listed below during Screening (Visit 1) and prior to enrollment at Visit 2:

- Blood Pressure: 80/50 to 140/90 mm/Hg
- Respiratory Rate: 8-20 breaths per minute
- Pulse: 50-120 beats per minute
- Temperature: 97.8°F to 99.1°F (36.5°C to 37.3°C)/average 98.6°F (37°C)

Vital signs will be taken pre- and post-dose at Visits 2, 4, 6 and 8. Pre-dose vital signs should be taken within 60 minutes before dosing. Post-dose vital signs should be taken at least 60 minutes after dosing, prior to discharge. Additional blood pressure and pulse measurements may be performed, as determined by the investigator, in order to ensure appropriate monitoring of subject safety and accurate recording of vital sign measurements. Any changes from baseline deemed clinically significant by the investigator are to be recorded as AEs.

The same method of blood pressure measurement (auscultatory or oscillometric) should be used and documented throughout the study for all subjects. In addition, the conditions of vital signs measurements should be controlled and as consistent as possible in order to minimize variability of the readings. It is advised that measurements be collected at a comfortable room temperature with little to no background noise, using the same (appropriately sized) cuff placed at the same location on the same arm. The cuff should have a bladder length that is 80% and a width that is at least 40% of arm circumference (a length-to-width ratio of 2:1).

The subject should be asked to remove all clothing that covers the location of cuff placement. The subject should not have exercised or consumed caffeine, alcohol, or nicotine within 30 minutes of collection. The subject should be comfortably seated, with the legs uncrossed, with feet flat on the floor, and the back and arm supported, such that the middle of the cuff on the upper arm is at the level of the right atrium (the mid-point of the sternum). The subject should be instructed to relax as much as possible for at least 5 minutes prior to collection. The subject should remain quiet during this time and throughout the measurement.

The bladder should be deflated (calibrated for oscillometric method or manually by auscultatory method) at a rate of 2-3 mmHg/sec (and the first and last audible sounds recorded as systolic and diastolic pressures) after at least 5 minutes of rest.

The use of automated devices for measuring pulse is acceptable, although, when done manually, pulse should be measured in the brachial/radial artery for at least 30 seconds. When the timing of these measurements coincides with a blood collection, blood pressure and pulse should be obtained prior to the nominal time of the blood collection.

12.3.1.3. Physical Examination

A complete physical examination, including measurements of weight, will be conducted by a qualified licensed physician, physician's assistant, or a nurse practitioner at the screening visit and at Visits 2 (Day 0), 6 (Day 28) and 10 (Day 56). Brief physical examinations, including measurements of weight, will be conducted at Visits 4 (Day 14), and 8 (Day 42) (see [Table 1](#)).

The complete physical examination will include a review of the following body systems:

- General appearance
- Skin
- Head, eyes, ears, nose, and throat
- Spine/neck/thyroid
- Musculoskeletal
- Respiratory
- Cardiovascular
- Neurological
- Abdomen (including liver and kidneys)

Any abnormalities or changes in intensity from baseline noted during the review of body systems should be documented in the medical record and reported on the appropriate eCRF. If a new clinically significant abnormal finding is reported after the baseline examination, it must be captured as an AE and documented on the appropriate AE eCRF. In addition, resolution of any abnormal findings during the study will be noted in the medical record and eCRF if clinically significant.

The brief physical examination will include a review of general appearance, skin, head, eyes, ears, nose, and throat, abdomen, joints and perianal area at a minimum, with other systems reviewed as medically needed. Measurement of weight will also be collected.

Subjects will remove their shoes before measurements of weight (in kg) are taken.

12.3.1.4. Electrocardiogram

A standard 12-lead ECG will be conducted by appropriate site staff as delegated by the PI and the results will be reviewed and verified by the PI or a qualified licensed physician delegated by the PI as shown in the Schedule of Assessments (see [Table 1](#)).

The 12-lead ECG will be performed after the subject has been supine for approximately 5 minutes. All ECG recordings will be identified with the subject number, subject initials, date, and time of the recording and will be included in the subject's study file.

The subject should be asked to remove all clothing that covers the location of lead placement. The subject should not have exercised or consumed caffeine, alcohol, or nicotine within 30 minutes prior to collection.

In some cases, it may be appropriate to repeat abnormal ECGs to rule out improper lead placement as contributing to the ECG abnormality. It is important that leads are placed in the same positions each time in order to achieve precise ECG recordings. One complete recording, including a 10-second rhythm strip, should be taken at each time point. It should be immediately assessed as a valid recording and if not valid, it should be repeated. All ECGs collected are to be entered in the eCRF.

All ECGs will be performed using the equipment supplied by the site. ECG recordings will be collected and a copy provided to the study sponsor.

The following parameters will be recorded on the appropriate eCRF: heart rate, PR, respiration rate (RR), QRS, and QT interval; corrected QT intervals using both the Bazett (QTcB) and Fridericia (QTcF) formulas will also be recorded. The investigator's assessment of the ECG tracing as normal or abnormal must be documented, and if abnormal, his/her determination of whether the abnormality is clinically significant will be documented on the tracing and recorded in the eCRF.

All ECG values that, in the investigator's opinion, show clinically relevant or pathological changes during or after termination of the investigational product are to be discussed with the medical monitor and reported as AEs and followed, as described in [Section 12.3.1.6.2](#).

12.3.1.5. Clinical Laboratory Assessments

12.3.1.5.1. Clinical Laboratory Tests

Samples for the following clinical laboratory tests will be collected at the time points specified in the Schedule of Assessments (see [Table 1](#)).

Hematology	Hemoglobin, hematocrit, red blood cell count, red blood cell indices, mean corpuscular hemoglobin, mean corpuscular hemoglobin concentration, mean corpuscular volume, platelet count (or estimate), and white blood cell count including differential
Serum chemistry	Albumin, total bilirubin, total protein, calcium, alkaline phosphatase, alanine aminotransferase, aspartate aminotransferase, gamma-glutamyl transferase, blood urea nitrogen, creatinine, creatine kinase, glucose, sodium, potassium, chloride, bicarbonate, lactate dehydrogenase, uric acid, eGFR, and C-reactive protein
Other	ADAs; LIGHT, cytokines (e.g. IL-1 beta, IL-6, IL-8, and TNF-alpha, and other exploratory cytokines), flow cytometry analysis of peripheral blood leukocytes and RNA sequencing
Fecal chemistry	Fecal calprotectin, C. difficile
Urinalysis	pH, specific gravity, hemoglobin, white blood cells, red blood cells, glucose, casts, protein, ketones, epithelial cells, crystals, mucous threads, bacteria, yeast, color, and appearance
Serum & Urine β-hCG test	For women of childbearing potential only
Urine drug screen (screening visit only as warranted)	Amphetamines, barbiturates, benzodiazepines, cocaine, opiates, phencyclidine, cannabinoids, propoxyphene and methadone.
Testing for previous biologics (for subjects requiring wash- out)	Commercial test to detect the serum concentrations of four of the common biologic drugs and biosimilars (infliximab [Remicade], infliximab-adba [Renflexis], infliximab-dyyb [Inflectra], adalimumab [Humira], adalimumab-adbm [Cyltezo], adalimumab-atto [Amjevita] vedolizumab [Entyvio] and ustekinumab [Stelara]). Note: Testing is not required for certolizumab pegol (Cimzia) as there is no commercially available test to determine serum concentration.

Laboratory specimens will be collected and analyzed at the laboratories specified in the study Laboratory Manual(s) or guidelines.

12.3.1.5.2. Sampled Blood Volume

The sampled blood volume to be taken from each subject is shown in [Table 3](#). (See [Section 12.3.2.1](#) for details regarding pharmacokinetic blood sampling.)

Table 3 Blood Samples Taken from Each Subject

Assessment		Sample Volume (mL)	Number of Samples	Total Volume (mL)
Safety	Hematology	2.0	6	12.0
	Clinical chemistry	3.5	6	21.0
MDGN-002 concentration and PK analysis (Pre-dose Day 0)		2.0	2	4.0
MDGN-002 concentration and PK analysis		2.0	9	18.0
Anti-drug Antibodies (ADA)		2.0	5	10.0
Flow Cytometry		3.0	3	9.0
RNA sequencing		2.5	3	7.5
Cytokines		3.5	3	10.5
LIGHT		2.0	3	6.0
Testing for previous biologics		6.0	1	6.0
Total mL		--	--	104.0

12.3.1.5.3. Tuberculosis (TB) testing

All subjects will be screened for tuberculosis using QuantiFERON-TB Gold (QFT) blood test, or tuberculin skin reaction test (PPD skin test) at screening. If the subject's PPD tine skin test is ≥ 5 mm, a chest x-ray is required to be performed to rule out active or latent pulmonary TB infection. Subjects will be excluded from the study if they have active or latent TB as demonstrated by any of the following:

- A positive QFT test result or a positive PPD skin test reaction ≥ 10 mm.
- Chest x-ray in which active or latent pulmonary TB cannot be ruled out.

12.3.1.5.4. Genotyping for Decoy Receptor 3

For patients with CD, 2 mL of saliva for genotyping will be collected in a designated collection vehicle according to the manufacturer's instructions.

Deoxyribonucleic acid (DNA) is isolated from the saliva samples from each study subject and then evaluated for genetic alteration in TNFRSF6B encoding for the protein DcR3 or alterations in at least one DcR3 network gene. All genotyping will be performed in a CLIA certified laboratory specified in the laboratory manual(s) and guidance(s). Any remaining DNA samples will be stored for future biomarker studies.

12.3.1.5.5. LIGHT, Cytokines, RNA Sequencing and Flow Cytometry Exploratory Analyses

Blood samples will be collected for exploratory analyses. Exploratory analyses may include but are not limited to of LIGHT biomarker, cytokines (e.g. IL-1 beta, IL-6, IL-8, TNF-alpha, and other exploratory cytokines), ribonucleic acid (RNA) sequencing; flow cytometry of peripheral blood leukocytes at visits specified in [Table 1](#). Exploratory biomarker analyses will be performed at the laboratories specified in the laboratory manual(s) and guidance(s).

12.3.1.5.6. Testing for Previous Biologics

An adequate wash-out period is required to avoid the potential for confounding the effects related to dosing with MDGN-002 following the prior use of other biologics. In order to allow for a shorter wash-out period, commercial tests available to identify the serum concentrations of biologics will be utilized. With the exception of Cimzia, a blood test will be administered to subjects undergoing wash-out 8 weeks after their last dose of biologic treatment to ensure that serum levels of any previous biologic treatments are below the level of detection. If the serum concentration of biologic treatment is undetectable (i.e., below the level of quantification) according to the respective, CLIA-validated commercial test, then the subject is deemed to have completed the wash-out period and will be able to proceed to Visit 2. If biologic treatment is detected, then the subject will complete a full 12-week wash-out period prior to proceeding to Visit 2. For subjects receiving the biologic certolizumab pegol (Cimzia) a 12-week wash-out is required.

12.3.1.5.7. Specimen Handling Requirements

The transmission of infectious agents may occur through contact with contaminated needles, blood or blood products and/or laboratory specimens. Consequently, appropriate blood, body fluid and specimen precautions should be employed by all study personnel involved in the collection and handling of specimens in both the clinic and laboratory settings. Refer to current recommendations of the appropriate authorities.

In addition to appropriate handling of subject samples, specific regulations exist regarding the shipment of biologic samples. Procedures and regulations for the packaging and shipping of infectious samples are outlined in the study Laboratory Manual(s). The investigator is responsible for ensuring that all study samples that are to be transported to another location are appropriately packed and shipped according to the applicable regulations.

12.3.1.5.8. Evaluation of Laboratory Values

The normal ranges of values for the clinical safety laboratory assessments will be provided by the responsible laboratory and submitted to Aevi Genomic Medicine, LLC prior to the beginning of the study. They will be regarded as the reference ranges upon which clinical decisions will be made.

If a laboratory value is out of the reference range, it is not necessarily clinically relevant, with the exception of those defined as exclusionary per [Section 9.2](#). The investigator must evaluate the out-of-range values and record his/her assessment of their clinical relevance in the appropriate eCRF.

All laboratory values which, in the investigator's opinion, show clinically relevant or pathological changes during or after termination of the treatment are to be discussed with the medical monitor and reported as AEs and followed, as described in [Section 12.3.1.6.2](#).

12.3.1.6. Adverse Events

12.3.1.6.1. Adverse Event Collection

The investigator is responsible for the detection and documentation of events meeting the criteria and definitions of an AE ([Section 12.3.1.6.2](#)) or SAE ([Section 12.3.1.6.6](#)) described below. At each visit, the subject will be allowed time to spontaneously report any issues since the last visit or evaluation. At each visit, the investigator will then monitor, ask about, and/or evaluate AEs using non-leading questions, such as:

- “How are you feeling?”
- “Have you experienced any issues since your last visit?”
- “Have you taken any new medications since your last visit?”

Any clinically relevant observations made during each visit will also be considered AEs.

12.3.1.6.2. Definition of Adverse Events, Period of Observation and Recording of Adverse Events

An AE is defined as any untoward medical occurrence in a clinical investigation subject administered a pharmaceutical product that does not necessarily have a causal relationship with the product. An AE can therefore be any unfavorable and unintended sign (including a new, clinically important abnormal laboratory finding), symptom, or disease, temporally associated with the product, whether or not related to the product.

All AEs are collected from the time of the informed consent is signed until the final safety follow-up visit (described in [Section 8.2.3](#)). This includes events occurring during the screening phase of the study, regardless of whether investigational product is administered. Where possible, a diagnosis rather than a list of symptoms should be recorded. If a diagnosis has not been made, then each symptom should be listed individually. All AEs should be captured on the appropriate AE eCRF and in source documents. In addition to AEs, unexpected benefits outside the investigational product indication should also be captured in the source documents and AE eCRF.

All AEs must be followed to closure (ie, the subject’s health has returned to his/her baseline status or all variables have returned to normal), regardless of whether the subject is still participating in the study. Closure indicates that an outcome is reached, stabilization is achieved (the investigator does not expect any further improvement or worsening of the event), or the event is otherwise explained. When appropriate, medical tests and examinations are performed so that resolution of an event(s) can be documented.

12.3.1.6.3. Severity of Adverse Events

The severity of AEs must be recorded during the course of the event, including the start and stop dates for each change in severity. An event that changes in severity should be captured as a new event. Worsening of pre-treatment events after initiation of the investigational product must be recorded as new AEs. For example, if the subject experiences mild, intermittent headaches prior to dosing with investigational product and the headache intensity increases to moderate after the

first dose of investigational product, a new AE of moderate intermittent headaches is to be recorded in the source documents and eCRF.

The medical assessment of clinical severity of an AE will be determined using the definitions outlined in Common Terminology Criteria for Adverse Events (CTCAE), Version 4.0 (Published May 28, 2009 with Version 4.0.3 on June 14, 2010 by the US Department of Health and Human Services, National Institutes of Health, National Cancer Institute):

Grade 1	Mild; asymptomatic or mild symptoms; or clinical or diagnostic observations only; or intervention not indicated
Grade 2	Moderate; or minimal, local or non-invasive intervention indicated; or limiting age-appropriate instrumental activities of daily living (ADL)
Grade 3	Severe or medically significant but not immediately life-threatening; or hospitalization or prolongation of hospitalization indicated; or disabling; or limiting self-care ADL.
Grade 4	Life-threatening consequences; or urgent intervention indicated.
Grade 5	Death related to AE

It is important to distinguish between severe AEs and SAEs. Severity is a classification of intensity whereas an SAE is an AE that meets serious criteria as described in [Section 12.3.1.6.6.2](#).

Please refer to the above-referenced CTCAE document for full description of CTCAE terms and instrumental and self-care ADLs.

12.3.1.6.4. Relationship Categorization

A physician/investigator must make the assessment of relationship to the investigational product for each AE. The investigator should decide whether, in his or her medical judgment, there is a reasonable possibility that the event may have been caused by the investigational product. If there is no valid reason for suggesting a relationship, then the AE should be classified as “not related.” Otherwise, the AE should be categorized according to the guidelines below. The causality assessment must be documented in the source document and the eCRF.

Not related	Exposure to Investigational Product (IP) has not occurred; OR The administration of IP and the occurrence of the AE are not reasonably related in time; OR The AE is considered likely to be related to an etiology other than the use of the IP; that is, there are no facts/evidence or arguments to suggest a causal relationship to the IP.
Possibly related	The administration of the IP and the occurrence of the AE are reasonably related in time AND The AE could not be explained equally well by factors or causes other than exposure to IP.
Probably related	The administration of IP and the occurrence of the AE are reasonably related in time AND The AE is more likely explained by exposure to IP than by other factors or causes.

IP=investigational product

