12.3.1.6.8. Reporting to Regulatory Agency, Institutional Review Board and Site

The sponsor or its designee is responsible for notifying the relevant regulatory authorities of related, unexpected SAEs.

In addition, the sponsor or its designee is responsible for notifying active sites of all related, unexpected SAEs occurring during all interventional studies across the development program.

The investigator is responsible for notifying the local IRB or the relevant local regulatory authority of all SAEs that occur at his/her site, as required.

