14.2.1. Case Report Forms

By signing the Investigator's Agreement ([Appendix 18.1](#)), the investigator agrees to maintain accurate eCRFs and source documentation as part of the case histories for all subjects who sign an Informed Consent Form.

Case report forms are considered confidential documents and should be handled and stored accordingly. The sponsor or its designee will provide the necessary training on the use of the specific eCRFs used during the study to ensure that the study information is captured accurately and appropriately.

To ensure data accuracy, eCRF data for individual subject visits should be completed as soon as possible after the visit. All requested information must be entered in the eCRF according to the completion guidelines provided by the sponsor or its designee. All data will have separate source documentation; no data will be recorded directly into the eCRF.

The eCRFs will be signed by the investigator or a subinvestigator to whom this authority has been delegated. These signatures serve to attest that the information contained in the eCRF is accurate and true.

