14.6. Changes to the Protocol

This protocol cannot be altered or changed except through a formal protocol amendment, which requires the written approval of Aevi Genomic Medicine, LLC. The protocol amendment must be signed by the investigator and approved by the IRB before it may be implemented. Protocol amendments will be filed with the appropriate regulatory agency(ies) having jurisdiction over the conduct of the study.

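### The second condition for *possibly related* is in substance the *probably related* test, so an AE explained equally well by the product and another cause has no row in the causality table (minor)

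*Protocol*

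**What the plan says.** Protocol section 12.3.1.6.4 opens by asking the investigator for a medical judgement on whether IP may reasonably have caused the AE. It continues: "If there is no valid reason for suggesting a relationship, then the AE should be classified as" *not related*. Every other AE is sent to the table, which has three rows:

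- *Not related*: no exposure; or the timing does not fit; or a third alternative in two halves, "The AE is considered likely to be related to an etiology other than the use of the IP", glossed (after a 'that is') as "there are no facts/evidence or arguments to suggest a causal relationship to the IP".
- *Possibly related*: the timing fits, and "The AE could not be explained equally well by factors or causes other than exposure to IP".
- *Probably related*: the timing fits, and "The AE is more likely explained by exposure to IP than by other factors or causes".

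SAP section 9.2 counts an AE as related if it is recorded as possibly or probably related, and this feeds Table 14.3.2.3. SAP section 5.7 analyses a blank relationship as related for AEs starting on or after the first dose. Protocol section 12.3.1.6.8 adds: "The sponsor or its designee is responsible for notifying the relevant regulatory authorities of related, unexpected SAEs". It does not say whose assessment, or which categories, make an SAE related. Protocol section 14.2.1 refers to completion guidelines ("All requested information must be entered in the eCRF according to the completion guidelines provided by the sponsor or its designee"), which are not among the documents.

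**The concern.** The two related categories are meant to be steps on a scale, yet they share the timing condition and their second conditions ask nearly the same thing. The lower step should hold AEs for which IP is one credible explanation among others. Its wording excludes exactly those.

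Such AEs are plausible here. Subjects may take corticosteroids, azathioprine, 6-MP or methotrexate during the study (Protocol section 10.2.1), and section 8.3 directs attention to infection and disease exacerbation. For events of that kind, IP and another cause can be about equally credible. The documents give no frequency.

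Safety is the primary objective, and the table of related TEAEs is one of its outputs. With up to 20 centres, different sites may also settle an unplaced AE differently.

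**Working it through.** The plan states no figure to reproduce, so the check is a case-by-case reading of the definitions.

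**Notation.** For an AE in an exposed subject with compatible timing, let D be how well IP explains it, O how well other causes explain it, and A mean that some fact, evidence or argument points to IP.

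**Conditions as written.**
- *Possibly related*, second condition: no other cause explains the AE as well as IP does, so D > O.
- *Probably related*, second condition: D > O.
- *Not related*, third alternative: first half O > D; second half no A.

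**Each state against each row.**

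| State | *Not related* | *Possibly* | *Probably* |
|---|---|---|---|
| D > O, with A | fails | met | met |
| D = O, with A | fails | fails | fails |
| D < O, with A | met only if the first half governs alone | fails | fails |
| D < O, without A | met | fails | fails |

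Row 1 is an overlap. SAP section 9.2 pools the two categories, so the overlap does not change whether the AE counts as related.

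Row 2 is the gap. The tie fails *not related* whether the first half governs, the second half governs, or both are needed: O is not greater than D, and A is present. The lead-in points the same way, because there is a valid reason to suggest a relationship.

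Row 3 is a smaller ambiguity. Its placement depends on which half of the third alternative governs. The gloss and the lead-in both speak against *not related*.

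**A more literal reading.** Suppose *possibly related* only requires that the explanations are not exactly equal (D ≠ O). The tie is still excluded, and AEs better explained by another cause, even without A, would now qualify. That reading does not rescue the row.

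**Consequence of each coding of a tie.**
- *Possibly related*: counted as related.
- Left blank: counted as related (SAP section 5.7).
- *Not related*: absent from the related-TEAE summaries. SAP section 9.2 keeps the most related occurrence within an SOC and preferred term, so a subject is lost from that line only if no other occurrence there is coded related.

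**The proposed wording, tested the same way.** Let *possibly related* require A and O ≥ D, and let the third *not related* alternative require no A. Row 1 becomes *probably* only, rows 2 and 3 *possibly* only, and row 4 *not related* only. Each state has one category. Restricting *possibly* to an exact tie (D = O) would place row 2 but leave row 3 open to *not related*, against the lead-in.

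**The case against.** The strongest reply is that the lead-in already decides the tie. It rests on reasonable possibility and reserves *not related* for AEs with no valid reason to suspect IP. That leaves *possibly* or *probably*, which the SAP pools, so an under-count needs a site to act against the lead-in. The completion guidelines may also clarify the categories already. This stands, and it is why the point is minor. It does not remove the error: the lead-in sends the AE to a table in which no row accepts it.

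Safeguards also limit the consequence. All AEs are listed. All SAEs go to the CRO and medical monitor within 24 hours regardless of relationship (Protocol section 12.3.1.6.6.3). The DMC reviews safety data. The stopping criteria in section 8.5 do not use these relationship categories, and nothing is tested formally.

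Three stronger readings are tempting, and the documents do not support them:

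- *That related TEAEs will be under-counted.* This depends on how sites code, which the documents do not show.
- *That regulatory notification is compromised.* Protocol section 12.3.1.6.8 does not tie its use of related to this table, so an effect there is possible but not shown.
- *That the effect has a size.* One subject would be 1/4 = 25.0 points in a CD cohort, 1/8 = 12.5 in the CD total and 1/6 = 16.7 in the UC group. But the count of one is assumed. One such subject in each CD cohort would make the CD total 2/8 = 25.0. The denominators are planned numbers, and replaced subjects who were dosed stay in the safety set. The arithmetic applies to any misclassified AE and is not evidence about this one.

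**Conclusion.** The definition of *possibly related* is wrong as written, and the error is minor. It in substance duplicates *probably related* and leaves a time-compatible tie without a category; this follows from the text under every reading tried. The harm is conditional: only coding a tie as *not related* removes it from the related-TEAE summaries, with a possible further effect on which SAEs are treated as related. The conclusion assumes that the completion guidelines do not already settle the matter. No size of effect can be derived from the documents.

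**What to change.** 1. Reword *possibly related* as the residual category under the lead-in. For example: the timing is reasonable, AND there is a reasonable possibility that IP caused the AE, but other factors or causes could explain it equally well or better.
2. Leave *probably related* and the SAP pooling unchanged.
3. State that the third *not related* alternative applies only when there are no facts, evidence or arguments for a causal relationship, as its own gloss and the lead-in already say.
4. Issue this wording to sites at once in the eCRF completion guideline, as a clarification of the lead-in, and carry it into the table at the next amendment. Section 14.6 is explicit: "This protocol cannot be altered or changed except through a formal protocol amendment". Waiting for the next amendment avoids a separate round of sponsor, investigator and IRB approval for a small change.
5. Before database lock, query post-dose AEs coded *not related* with reasonable timing. Put the same question to each: which alternative applied and, if the third, whether any argument for IP existed. Select by this uniform rule, not by asking sites which assessments they remember as affected. Keep the investigator's recorded assessment in the AE listing beside any change.

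The cost is a small number of queries in about 14 subjects. Revisiting causality in an open-label study carries some risk of bias, which the uniform rule limits but does not remove. The related-AE count may rise slightly.
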